## 6.5.5 Distance Visual Acuity after 8 Weeks and 56 Weeks on Randomized Treatment

An analysis of covariance (ANCOVA) will be performed to compute the difference in mean change in amblyopic-eye distance logMAR VA after 8 weeks and 56 weeks between the sequential and simultaneous treatment groups, adjusted for baseline amblyopic eye distance VA, and a 2-sided p-value and an FDR-adjusted confidence interval will be constructed on the treatment group difference for each time point.

## 6.5.6 Binocularity

Binocularity will be assessed on an ordered scale combining the results of the Randot Preschool Test, Randot butterfly, and Worth 4-Shape at near. Results of each individual test also will be tabulated at baseline and at the final study visit according to treatment group.

- The possible levels of binocularity will be 40, 60, 100, 200, 400, 800 seconds of arc (Randot Preschool test), 2000 seconds of arc (Randot butterfly), binocular perception by W4D (4 or 5 lights), or no binocular perception by W4D (2 or 3 lights). This yields an ordered binocularity scale with 9 ordered levels. The change in binocularity levels for each test will be tabulated and
- 1054 compared between treatment groups using the exact Wilcoxon rank-sum test. The proportion of

participants in each treatment group unable to perform testing will be tabulated but these participants will not be included in the analysis of change.

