## 3. Binocularity Testing:

- Gross binocularity will be tested in current spectacle correction at near using the hand-held Worth 4-Shape test held at 40 cm.
- Stereoacuity will be tested at near in current spectacle correction using both the Randot Butterfly and Randot Preschool stereoacuity tests.

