## **6.5** Secondary Efficacy Outcomes

All secondary outcomes involving amblyopic eye distance VA will use the ITT dataset with amblyopic eye distance VA imputed when missing. Secondary outcomes not involving amblyopic eye distance VA will use observed data, with no imputation for missing data.

For secondary outcome comparisons that are based on a parametric statistical model, all model assumptions will be checked, and if violated, data transformation or a non-parametric alternative will be used instead.

	JAEB CENTER FOR HEALTH RESEARCH
964	The distribution of all secondary outcomes will be tabulated at randomization and the outcome
965	visit for each randomized treatment group and described using descriptive statistics.
966	
967	Treatment group comparisons on secondary clinical outcomes will be controlled using the false
968	discovery rate (FDR) method at 5% and to adjust p-values and confidence intervals for
969	multiplicity.
970	
971	6.5.1 Pediatric Eye Questionnaire (PedEyeQ)
972	Rasch scores for each questionnaire item will be obtained from published look-up tables
973	available at www.pedig.net, and used to calculate a score for each participant and a separate
974	treatment group mean for each of the PedEyeQ domains of the Child, Proxy, and Parent
975	PedEyeQ at randomization and at each visit. Scores will also be converted to a 0-100 scale to
976	aid in interpretation.

976 977

978

979

980 981

982

983 984

985

986

987

988

989 990

991

992

- Child PedEyeQ:
  - Functional Vision
    - o Bothered by Eyes and Vision
  - Social
  - o Frustration / Worry
- Proxy PedEyeQ:
  - Functional Vision
  - o Bothered by Eyes and Vision
  - o Social
  - o Frustration / Worry
  - o Eye care
- Parent PedEyeO:
  - o Impact on Parent and Family
  - Worry about Child's Eye Condition
  - Worry about Self-perception and Interactions
  - Worry about Functional Vision

993 994 995

996 997

998

999

1000 1001

1002

Comparisons of interest, following the hypotheses detailed in the Background section are as follows:

- Comparison of domain scores between treatment groups at 8 weeks (the first follow-up visit, before the sequential group has the opportunity to start patching and is still in spectacle correction).
- Comparison of domain scores between treatment groups at the primary outcome visit defined as in *section 6.4*.
- Comparison of domain scores between treatment groups at the conclusion of the study (56 weeks).

1003 1004 1005

1006

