## **6.5.7** Contrast Sensitivity

Contrast sensitivity scores range from unable (<0.90), and then from 0.90 to 2.05 (by 0.05 log contrast sensitivity units). An analysis of covariance (ANCOVA) will be performed to compute the difference in mean change in amblyopic-eye log contrast sensitivity units between the sequential and simultaneous treatment groups, adjusted for baseline amblyopic eye contrast sensitivity, and a 2-sided p-value and FDR-adjusted confidence interval will be constructed.

Test-retest reliability will be evaluated at the 8-week post-randomization visit. The difference between the initial and repeat contrast sensitivity score of the left eye will be calculated and evaluated across the age distribution to see if it is appropriate to combine data from both age cohorts, or if the data should be analyzed within subgroups defined by age. Analyses (overall or by age) will then evaluate the test/retest differences in contrast sensitivity as a function of the mean value for the initial and repeat test (Bland-Altman type analyses). Confidence intervals for the upper and lower limits of agreement will be calculated either overall or within subgroups defined by the mean test/retest contrast sensitivity score if the data suggest there is a difference across the distribution of scores.

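### The binocularity comparison in 6.5.6 leaves out the baseline level: a valid test, but one that gives up precision which baseline adjustment would recover at no cost in data

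*Protocol*

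**What the plan says.** Section 6.5.6 builds one ordered scale from the Randot Preschool, Randot Butterfly and Worth 4-Shape tests: "This yields an ordered binocularity scale with 9 ordered levels". It continues "The change in binocularity levels for each test will be tabulated and" "compared between treatment groups using the exact Wilcoxon rank-sum test". No covariate or stratification is named. On missing results, the section says that "participants in each treatment group unable to perform testing will be tabulated but these participants will not be included in the analysis of change", and section 6.5 says that secondary outcomes not involving "amblyopic eye distance VA will use observed data, with no imputation for missing data".

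The baseline value is scheduled. Under Binocularity Testing, section 3.1.3 states "Gross binocularity will be tested in current spectacle correction at near using the hand-held Worth 4-Shape test held at 40 cm" and "Stereoacuity will be tested at near in current spectacle correction using both the Randot" Butterfly and Preschool tests. The visit schedule marks binocularity at the Spectacle Baseline / Randomization Visit and at every follow-up visit.

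Other outcomes measured at baseline are adjusted for it. Contrast sensitivity (6.5.7) is "adjusted for baseline amblyopic eye contrast" sensitivity. Baseline VA enters the primary analysis (6.4), the binary VA outcomes (6.5.3) and VA at 8 and 56 weeks (6.5.5). Baseline domain score enters the PedEyeQ models (6.5.1).

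**The concern.** Binocularity is a listed between-arm secondary efficacy endpoint, and the protocol fixes its test by name. Subtracting the baseline is not the same as adjusting for it. A change score carries the measurement noise of both visits. A model for the follow-up level with baseline as a covariate removes only the part of the follow-up variation that baseline predicts.

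Two features of this scale add to the point. It is bounded: a child at 40 seconds of arc cannot improve and a child without binocular perception cannot worsen, so change depends on where the child starts. It is also only ordered, and subtracting level numbers treats every one-level step as equal before the ranks are taken.

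At stake is the chance of detecting a real arm difference in binocularity. That chance is already reduced by the exclusion of children who cannot do the tests and by the 5% false discovery rate control over the secondary outcomes.

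**Working it through.** **Is there a plan figure to reproduce?** Not for binocularity. The power statements in 6.12.4 concern VA only. They do recompute closely: 2 × (1.7 × (1.960 + 1.645) / 0.75)² gives 134 per arm, 268 in total (270 with t-based power), against the stated 272. Power for a 0.67-line difference at 136 per arm is 90.1% against the stated 90%. Neither carries over to binocularity, so everything below rests on assumed inputs.

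**Linear-model approximation.** Assume equal variance σ² at baseline and follow-up, and correlation ρ.
- Variance of the change score: 2σ²(1 − ρ).
- Residual variance with baseline as covariate: σ²(1 − ρ²).
- Ratio, adjusted over change: (1 − ρ²) / (2(1 − ρ)) = (1 + ρ) / 2, which is below 1 for any ρ below 1.
- If the change test has 80% power at two-sided 0.05, adjusted power = Φ((1.960 + 0.842) / √((1 + ρ)/2) − 1.960).

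| Assumed ρ | Variance ratio | Adjusted power | Gain in points |
|---|---|---|---|
| 0.3 | 0.65 | 93.5% | 13.5 |
| 0.5 | 0.75 | 89.9% | 9.9 |
| 0.7 | 0.85 | 86.0% | 6.0 |
| 0.8 | 0.90 | 84.0% | 4.0 |
| 0.9 | 0.95 | 82.0% | 2.0 |

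The reference power is also an assumption. If the change test had 90% power, the gains at ρ of 0.5, 0.7 and 0.9 would be 6.3, 4.0 and 1.4 points.

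**Simulation on a 9-level scale.** The formula is not a theorem for rank tests on a tied, bounded scale, so rank-sum on change was compared with baseline-adjusted rank ANCOVA. Settings: latent normal values cut into 9 levels, 30% of children in the lowest level at baseline, 3,000 trials per setting, and an effect that shrinks as ρ rises (0.402 SD at latent ρ 0.3 down to 0.152 SD at 0.9). At 136 per arm:
- ρ 0.3: 78.0% against 91.7%
- ρ 0.5: 75.4% against 85.7%
- ρ 0.7: 72.9% against 79.1%
- ρ 0.8: 67.5% against 73.2%
- ρ 0.9: 62.1% against 66.6%

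With no true effect, rejection rates were 4.8% to 5.3% for the rank-sum test and 4.3% to 5.4% for rank ANCOVA. With 110 per arm and a correspondingly larger effect, the results were similar (75.4% against 85.2% at ρ 0.5; 70.9% against 79.1% at ρ 0.7). With all nine levels equally common at baseline, the gains were larger, about 13 to 23 points.

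**Where the gain disappears.** A further simulation put 25% in the lowest level, with 136 per arm and 1,000 trials. At a 0.30 SD effect it gave 60% against 74% (ρ 0.5), 81% against 88% (ρ 0.7), 92% against 95% (ρ 0.8) and 99.8% against 99.7% (ρ 0.9, where both tests have almost full power). At a 0.10 SD effect it gave 11% against 15%, 14% against 16% and 21% against 22% at ρ of 0.5, 0.7 and 0.8.

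**The case against.** The strongest reply is that nothing here is wrong. An exact rank test suits ordinal data with many ties, its type I error is correct, and the protocol nowhere says that binocularity must be adjusted. VA, PedEyeQ and contrast sensitivity are modelled as continuous scores, so treating an ordinal outcome differently is defensible. All of this stands. It makes the point one of efficiency, and it does not supply a reason to leave the baseline out.

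A reader might infer a definite loss, say 5 to 14 points of power. The documents do not support that. They give no correlation, level frequencies or effect size for binocularity, and the range moves with each of them.

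A reader might also infer that baseline is available for everyone. It is scheduled for everyone, but 6.5.6 expects some children to be unable to do the tests. Section 6.12.4 expects 10% loss to follow-up or withdrawal, and non-VA outcomes are not imputed. The analysed number will be below 136 per arm, and an adjusted analysis needs the same observed baseline as a change analysis does.

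Finally, the words on change for each test could be read to mean that the combined scale is never compared. That reading is too strong: the sentence follows directly on the definition of the combined levels, and change on that scale is a plausible meaning. The wording is ambiguous and should be settled. The 9-level simulations apply only if change on the combined scale is what is tested.

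**Conclusion.** The point holds as a loss of efficiency in a secondary outcome tested by a valid method. Section 6.5.6 names an unadjusted test on change, although the baseline value is collected under the protocol and the comparable outcomes use theirs.

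At moderate correlation the expected gain from adjustment is useful, roughly 6 to 10 points of power at correlations of 0.7 to 0.5 when the unadjusted test has 80%. At correlations of 0.8 to 0.9 it is about 4 to 2 points on the same approximation, and it can be near zero when the effect is small or power is already high. The direction rests on a correlation below 1 and similar variances at the two visits. The size rests on inputs that the protocol does not give. The conclusions on VA are unaffected.

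**What to change.** In 6.5.6, state that the follow-up level on the combined 9-level scale is compared between arms with adjustment for baseline level, among children with observed baseline and follow-up, separately within each age cohort. Rank ANCOVA is sufficient if only a p-value is needed. A proportional-odds model with treatment and baseline level is the choice if an effect estimate and an FDR-adjusted confidence interval are wanted. Keep the per-test change tabulations as descriptive, which also settles what is being tested.

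This takes a sentence or two in the protocol and a matching entry in the SAP, with no new data or visits. There are small costs:
- The p-value is no longer exact. That matters little at about 136 per arm, but more in the older cohort if it is small.
- Rank ANCOVA gives no directly interpretable effect estimate.
- The proportional-odds assumption must be checked. Section 6.5 sends parametric models with violated assumptions to a transformation or a non-parametric alternative, so rank ANCOVA should be named as the fallback.

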## **6.5.7** Contrast Sensitivity

Contrast sensitivity scores range from unable (<0.90), and then from 0.90 to 2.05 (by 0.05 log contrast sensitivity units). An analysis of covariance (ANCOVA) will be performed to compute the difference in mean change in amblyopic-eye log contrast sensitivity units between the sequential and simultaneous treatment groups, adjusted for baseline amblyopic eye contrast sensitivity, and a 2-sided p-value and FDR-adjusted confidence interval will be constructed.

Test-retest reliability will be evaluated at the 8-week post-randomization visit. The difference between the initial and repeat contrast sensitivity score of the left eye will be calculated and evaluated across the age distribution to see if it is appropriate to combine data from both age cohorts, or if the data should be analyzed within subgroups defined by age. Analyses (overall or by age) will then evaluate the test/retest differences in contrast sensitivity as a function of the mean value for the initial and repeat test (Bland-Altman type analyses). Confidence intervals for the upper and lower limits of agreement will be calculated either overall or within subgroups defined by the mean test/retest contrast sensitivity score if the data suggest there is a difference across the distribution of scores.

## 6.6 Safety

The PEDIG DSMC will review safety data tabulated by treatment group at each of its semi-annual meetings and can request formal statistical comparison of any safety outcome at any time if they have cause for concern. As type II error is more of a concern than type I error in safety analyses, we will use p<0.05 without adjustment for multiplicity to define statistical significance in all safety analyses.

#### 6.6.1 Distance VA in Fellow Eye

The mean change in fellow-eye distance VA from randomization to the last visit while on randomized treatment (using the mean of test and retest if done or initial test if retest not done at each visit) will be calculated and compared between treatment groups using ANCOVA with adjustment for baseline VA, and a 2-sided p-value and 95% confidence interval will be constructed on the estimated treatment group difference.

The proportion of participants with loss of 2 or more logMAR lines (10 or more letters) of VA in the fellow eye from randomization to their last visit (using the mean of test and retest if done or initial test if retest not done at each visit) while on randomized treatment will be reported for each treatment group and compared using Barnard's exact test.

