Primary Endpoint	
 
The primary efficacy endpoint will be mean change in amblyopic eye logMAR distance VA between randomization and VA at completion of randomized treatment or at 56 weeks, whichever is earlier.
 
The primary endpoint for each participant is defined as:
 
1. Amblyopic eye VA (calculated as mean of test and retest) at the last visit that was the basis for a "stable resolved" or "stable residual" determination (in the sequential group, stable residual amblyopia criteria can be reached only after patching has been instituted); or
 
2. Amblyopic-eye VA at 56 weeks (calculated as mean of test and retest) in those completing a 56 week visit without ever meeting criteria for "stable resolved" or "stable residual" amblyopia (if retest missing at 56 weeks, the single test value will be used).
 
To determine if the following endpoints differ between simultaneous treatment and sequential
 

Secondary Objectives/Endpoints	treatment groups.  Efficacy:  Child and parental health-related quality of life (HRQOL) domain scores as measured by PedEyeQ.  Proportion of participants with improvement of amblyopic eye distance VA of 2 or more logMAR lines (>=10 letters if E-ETDRS), using the primary endpoint as defined above.  Time to stable resolved amblyopia.  Amblyopic-eye distance VA (calculated as mean of test and retest) after 8 weeks.  Amblyopic-eye distance VA (calculated as mean of test and retest) at 56 weeks for all participants.  Binocularity by Randot Preschool Stereotest, Randot Butterfly Stereotest, and Worth 4 Shape Testing.  Monocular contrast sensitivity.  Safety:  Worsening of best-corrected fellow-eye distance VA of 0.2 logMAR lines or more at any time during the study from baseline (based on mean of test and retest, or initial test if retest not done).  Proportion of participants who develop a new strabismus.

	Proportion of participants who develop mild moderate and severe skin imitation from
	
 
Proportion of participants who develop mild, moderate, and severe skin irritation from patching.
 

	To evaluate the following endpoint within simultaneous treatment and sequential treatment groups:
	Recurrence of amblyopia in those who have resolved (defined as a 0.2 or more logMAR reduction and IOD of 0.2 logMAR or more from value at visit of resolution).

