## **6.6.2** Ocular Alignment

The proportion of participants with development of new strabismus by cover testing at distance or near (no heterotropia at baseline and the presence of near and/or distance heterotropia at a subsequent visit) or an increase from baseline  $\geq 10\Delta$  by PACT in a pre-existing strabismus at any time on randomized treatment during the study will be reported by treatment group and compared using Barnard's exact test.

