#### 1101 6.6.3 Skin Irritation from Patching 1102 The proportion of participants with skin irritation from patching reported as "severe" at any time 1103 during the study, using the severe, moderate, or mild scale, will be tabulated for each randomized 1104 treatment group. 1105 1106 **Adherence with Randomized Treatment** 1107 1108 Adherence with Spectacles 1109 Data from the parental calendar of spectacle wear will be used to calculate a subjective measure 1110 of adherence. The average % of spectacle treatment completed across visits will be defined by the investigator as poor (<25%), fair (25% to <50%), good (50% to <75%), or excellent 1111 (>=75%), based on investigator impression of the total hours of spectacle wear since the last 1112 1113 study visit. 1114 1115 Adherence with Patching 1116 Data from the occlusion dose monitor (ODM) will be used to calculate an objective measure of 1117 adherence. The proportion of patching completed will be defined as the total hours of patching 1118 divided by the total hours of prescribed patching over a specified period of time. 1119 1120 6.7.1 Adherence within the Sequential Treatment Group 1121 1122 **6.7.1.1** While Wearing Spectacles Alone 1123 The adherence with spectacles between randomization and the visit at which VA stability or 1124 resolution with spectacles alone was achieved will be calculated as described in section 6.7 for 1125 each participant and the distribution within those randomized to sequential treatment will be 1126 summarized. 1127 1128 Average adherence with spectacle wear over the total number of study visits will be 1129 dichotomized based on having excellent (an average of 3 or higher) adherence, and the mean improvement in amblyopic eye VA will be compared between the 2 groups (average adherence 1130 of $\geq 3$ or higher versus average of < 3) thus defined using ANCOVA, with adjustment for baseline 1131 age and amblyopic eye VA. 1132 1133 1134 6.7.1.2 While Wearing Spectacles and Patching After Stable VA on Spectacles Alone 1135 For participants who initiate patching after reaching stable amblyopic eye VA with spectacles 1136 alone, their adherence with patching between the visit at which patching was initiated and the 1137 visit at which a "stable resolved" or "stable residual" determination was made while on 1138 spectacles and patching will be calculated as described in section 6.7 for each participant, and the 1139 distribution within those randomized to sequential treatment will be summarized. 1140

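### The fellow-eye safety endpoint is listed as worsening at any time in the study, but section 6.6.1 analyses only the last visit on randomized treatment; the skin-irritation endpoint is narrowed in a similar way

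*Protocol*

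**What the plan says.** The Protocol Summary, under safety endpoints, lists "Worsening of best-corrected fellow-eye distance VA of 0.2 logMAR lines or more at any time during the study from baseline". It also lists "Proportion of participants who develop mild, moderate, and severe skin irritation from" patching.

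Section 6.6.1 gives two fellow-eye analyses, both tied to one visit per child:

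- The continuous analysis is "The mean change in fellow-eye distance VA from randomization to the last visit while on randomized treatment".
- The binary analysis takes the proportion "with loss of 2 or more logMAR lines (10 or more letters) of VA in the fellow eye from randomization to their last visit", which "while on randomized treatment will be reported for each treatment group and compared using Barnard's exact test".

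The neighbouring safety outcomes are counted differently. Section 6.6.2 counts new or increased strabismus "at any time on randomized treatment during the study will be reported by treatment group". Section 6.6.3 tabulates "The proportion of participants with skin irritation from patching reported as" severe at any time during the study. It names the three-grade scale but reports only the top grade.

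Three other parts of the protocol bear on this. Section 6.6 states that type II error is the greater worry in safety analyses and therefore applies no multiplicity adjustment. Section 4.4.1 has distance acuity tested in each eye at every study visit. Sections 4.1 and 4.2 keep children on 8-weekly visits to 56 weeks after they complete randomized treatment.

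**The concern.** Two current parts of the protocol define one safety endpoint in incompatible ways, and a later analysis document can follow only one of them. Nothing in section 6 delivers the endpoint that the Summary promises, because the mean-change analysis uses the same visit as the binary one.

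Two kinds of event fall outside the comparison: a loss that has recovered by the last on-treatment visit, and a loss first seen after release. Leaving them out sits badly with the stated priority on avoiding missed harms. It also makes fellow-eye acuity the only one of the three safety outcomes in section 6.6 that is not counted on an any-time basis.

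The skin endpoint has the same kind of gap: two of the three listed grades have no planned tabulation.

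**Working it through.** The protocol gives no rate, power or sample size for fellow-eye loss, so there is no stated figure to reproduce. The main check compares the texts.

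**1. Definitions side by side**

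| Outcome | Protocol Summary | Section 6.6 |
|---|---|---|
| Fellow-eye loss | any time during the study | last visit on randomized treatment (6.6.1) |
| Strabismus | new strabismus, no time frame | any time on randomized treatment (6.6.2) |
| Skin irritation | mild, moderate, severe | severe only, any time during the study (6.6.3) |

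The fellow-eye row conflicts on timing and the skin row on content.

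**2. Threshold**

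Section 2.3 criterion 5 equates 3 logMAR lines with 0.3 logMAR and 15 letters. So 1 line = 0.1 logMAR = 5 letters, and the section 6.6.1 threshold of 2 lines = 0.2 logMAR = 10 letters. Read literally, 0.2 lines would be 0.02 logMAR, or 1 letter. The Summary makes the same slip in its key inclusion criteria, where the interocular difference is given as 0.3 logMAR lines although section 2.3 has 3 lines. The intended threshold is 0.2 logMAR in both places.

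**3. Events that could be dropped (assumptions only)**

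Let p be the true any-time rate and m the share of losses that recover before, or arise after, the last on-treatment visit. Section 6.6.1 then counts 136 × p × (1 − m) per arm in the younger cohort (136 per group, section 6.12.4).

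- p = 2%: 2.7 events occur; 2.0 (m = 25%) to 0.7 (m = 75%) are counted.
- p = 5%: 6.8 occur; 5.1 to 1.7 are counted.
- p = 10%: 13.6 occur; 10.2 to 3.4 are counted.

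Neither p nor m is in the protocol. These lines show how the count depends on m and are not a forecast.

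**4. Cost of any-visit counting (assumptions only)**

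Assume no true change and independent normal error in each acuity (mean of test and retest) with SD 0.06 to 0.10 logMAR. At one visit the chance of an apparent loss of 0.2 or more is 1 − Φ(0.2 / (√2 × SD)). The any-visit columns come from 400,000 simulated children, each with one baseline shared across visits.

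| SD | Last visit | Any of 2 visits | Any of 4 | Any of 7 |
|---|---|---|---|---|
| 0.06 | 0.9% | 1.7% | 3.1% | 4.8% |
| 0.08 | 3.9% | 6.8% | 11.4% | 16.4% |
| 0.10 | 7.9% | 13.4% | 21.2% | 28.9% |

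Over seven visits an any-visit rule flags about four to five times as many unchanged children as a single visit does. The definitions are not interchangeable, and an any-visit count needs a confirmed-loss count beside it.

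**The case against.** The strongest reply is that section 6.6.1 makes a defensible choice. The last on-treatment visit closes the period of assigned treatment, uses one measurement and limits noise. Any-visit counting to 56 weeks brings in treatment at investigator discretion (sections 4.1 and 4.2) and acuity that may be tested unmasked after the primary outcome (schedule of visits, footnote). Section 5.4.2 also calls sound-eye loss extremely unlikely when that eye has several hours without occlusion each day, so false flags could outnumber real events. All of this stands as a limit on the remedy. It does not remove the contradiction, and section 6.6.2 shows a middle course in any-time counting while on randomized treatment.

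A reader might infer more than the protocol supports:

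- **That the last-visit rule is blind to reversible loss.** Section 5.4.2 says such loss is almost always reversible. It does not say that the loss recovers while patching continues. A loss that persists to the last on-treatment visit is counted. Nor does that section rank sound-eye loss above the other patching risks that it lists.
- **That detection differs between arms by a known amount.** Sequential children with residual amblyopia must meet non-improvement twice and simultaneous children once, so the number of on-treatment visits may differ. Turning that into detection probabilities requires assumptions about how long a loss lasts. It also requires leaving out spectacles-only visits, which carry no patching exposure. The protocol supplies neither the durations nor the visit counts.
- **That the two thresholds differ tenfold.** This is a unit slip, as shown above.
- **That the dropped losses are never seen.** Section 6.6 has the committee review tabulated safety data semi-annually, with formal comparison of any safety outcome on request. That is discretionary monitoring and does not replace the listed endpoint.

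**Conclusion.** The point holds as an inconsistency between listed endpoints and planned analyses. The fellow-eye endpoint is any-time in the Summary and last-on-treatment-visit in section 6.6.1. The skin endpoint has three grades in the Summary and one in section 6.6.3. Confidence in both mismatches is high because they can be read directly from current text.

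The size in events is unknown; it depends on a loss rate and a recovery pattern that the protocol does not give. The primary analysis and the sample size of 272 are unaffected. It is worth correcting because it changes what the safety comparison counts, and the acuity data needed are already collected at every visit.

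**What to change.** 1. In section 6.6.1, define the binary endpoint as a fellow-eye loss of 0.2 logMAR or more (2 lines, 10 letters) from baseline at any study visit. Report it for visits on randomized treatment, as in section 6.6.2, and for all visits through 56 weeks.
2. As supplements, report losses confirmed at the next visit and the last on-treatment value now specified.
3. In the Protocol Summary, change 0.2 logMAR lines to 0.2 logMAR for this endpoint.
4. In section 6.6.3, tabulate mild, moderate and severe skin irritation by group.

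The cost is protocol and analysis-plan wording plus a few more table rows; no new measurements are needed. The any-visit figures will contain more test noise, and the 56-week figures will mix in discretionary treatment and possibly unmasked acuity. The on-treatment and confirmed-loss results should therefore appear beside them, with that limitation stated.
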